## 6.3 Screen Failures

Screen failures are defined as participants who consent to participate in the clinical trial but are not subsequently randomly assigned to the study intervention or entered in the study. A minimal set of screen failure information is required to ensure transparent reporting of screen failure participants, to meet the Consolidated Standards of Reporting Trials (CONSORT) publishing

requirements. Minimal information includes informed consent, demography, eligibility criteria and screen failure details, including screening laboratory results.

Subjects who fail to qualify for the study may be considered for rescreening at the discretion of the Investigator, if it is considered that the subject's status has changed, and the subject may now qualify for the study. A new informed consent is required to be signed prior to every rescreening. Rescreened subjects will be assigned a new screening number.

Any subject who is randomized to study intervention but does not receive study drug will be considered an early termination.

## **7.0 STUDY INTERVENTION**

### **7.1 Study Intervention(s) Administration**

#### **7.1.1 Study Intervention Description**

Ferric citrate will be supplied as tablets for oral administration containing 1 g ferric citrate (210 mg of ferric iron).

Placebo will be supplied as tablets, matching in color and size to ferric citrate.

Subjects should take the assigned study drug orally with meals or snacks or within 1 hour before or after their meals or snacks.

Missed doses should not be taken if greater than 1 hour from meals.

#### **7.1.2 Dosing and Administration**

Study drug is not intended to be used as a treatment for either serum phosphorus or iron repletion. Management of serum phosphorus and iron sufficiency will be directed at the discretion of the treating physician and/or Investigator independent of study drug with the only restriction being that subjects cannot be prescribed commercial Auryxia (ferric citrate).

Subjects will be randomized in a 1:1 ratio to receive either ferric citrate or placebo. All subjects will be instructed to take study drug at a fixed dose of 2 tablets per meal or snacks, up to three times per day. The maximum dose is 6 tablets/day. No additional tablets (beyond a total of 6/day) should be taken. Tablets should not be crushed or chewed.

Every effort will be made to provide study drug to subjects at the Day 1 visit. If there are delays related to shipment from the USRC Rx pharmacy, study drug will be provided to subjects within 12 days of the Day 1 visit. Dosing will begin upon receipt of study drug with the next meal/snack. This would not be considered a protocol deviation.

#### **7.1.2.1 Dose Adjustment**

No titration of study drug will be performed other than for issues of tolerability or safety.

It is expected that the Investigator will monitor serum phosphorus and iron indices per generally recognized standard of care for individuals with advanced CKD. The monitoring of iron indices

and serum phosphate is required at least every 3 months and failure to monitor these parameters will be considered a protocol deviation.

Required dose adjustments for low serum phosphorus are as follows:

- If serum phosphorus is  $<3.0$  mg/dL captured by a single value, the study drug, and any other prescribed phosphate lowering therapy, should be temporarily held until such time as serum phosphorus is  $\geq 3.0$  mg/dL at which time study drug may be resumed at a dose that is approximately equivalent to 50% of the previous total daily dose. The reduction in dose relative to meals or snacks is at the discretion of the investigator as long as it represents a total dose reduction of 50%. Repeat assessment of serum phosphorus will be at the discretion of the Investigator. This assessment must occur at the next scheduled visit (which may be up to three months), or it may also be performed earlier. Other prescribed phosphate lowering therapy may be resumed per investigator discretion when serum phosphorus is  $\geq 3.0$  mg/dL.

Required dose adjustments for high TSAT are as follows:

- If TSAT is  $>45\%$  and  $\leq 50\%$ , captured by a single laboratory value, the study drug should be reduced by 1 tablet per meal or snack (reduce the dose by the equivalent of 50%). Any other prescribed oral or IV iron therapy should be stopped.

If TSAT is  $>50\%$ , captured by a single laboratory value, the study drug, and any other prescribed oral or IV iron therapy, should be temporarily held until such time as TSAT is  $\leq 50\%$  (captured by a single laboratory value) at which time study drug may be resumed at a dose that is equivalent to 50% of the previous total daily dose. The reduction in dose relative to meals or snacks is at the discretion of the investigator as long as it represents a total dose reduction of 50%. Repeat assessment of iron indices will be at the discretion of the Investigator. This assessment must occur at the next scheduled visit (which may be up to three months), or it may also be performed earlier.

If after a 50% reduction in total daily dose of study drug, the TSAT is  $>50\%$ , the study drug should be temporarily held. Subsequent study visits including the Follow Up visit (Visit 6) should continue to be conducted as per the SoA (regardless of study drug administration). When TSAT is  $\leq 50\%$ , study drug may be resumed. Other prescribed oral or IV iron therapy may be resumed per investigator discretion when TSAT is  $\leq 45\%$ .

Required dose adjustments for high ferritin are as follows:

- If serum ferritin is  $>500$  ng/mL, captured by a single laboratory value, the study drug, and any other prescribed oral or IV iron therapy, should be temporarily held until such time as ferritin is  $\leq 500$  ng/mL (captured by a single laboratory value) at which time study drug may be resumed at a dose that is equivalent to 50% of the current total daily dose. The reduction in dose relative to meals or snacks is at the discretion of the investigator as long as it represents a total dose reduction of 50%. Repeat assessment of iron indices will be at the discretion of the Investigator. This assessment must occur at the next scheduled visit (which may be up to three months), or it may also be performed earlier.

- If after a 50% reduction in total daily dose of study drug, the serum ferritin is  $>500$  ng/mL, the study drug should be temporarily held. Subsequent study visits including the Follow Up visit (Visit 6) should continue to occur per the SoA (regardless of study drug administration). When serum ferritin is  $\leq 500$  ng/mL, study drug may be resumed. Other prescribed oral or IV iron therapy may be resumed per investigator discretion when ferritin is  $\leq 500$  ng/mL.

Both TSAT and ferritin laboratory values must be within ranges defined above prior to resumption of study drug.

Study drug may be titrated downward at any time during the treatment period at the discretion of the Investigator for adverse reactions determined to be related to study drug.

**There is no minimum allowable dose of study drug, and the Investigator has discretion to resume dosing up to 6 tablets/day based on subject acceptance when possible (and when TSAT, ferritin, and phosphorus values are within protocol-defined ranges).**

All dose adjustments should be captured in the subject specific source documentation and the eCRF.

## **7.2 Preparation/Handling/Storage/Accountability**

### **7.2.1 Acquisition and Accountability**

Akebia Therapeutics will supply study drug to a centralized pharmacy known as USRC Clinical Pharmacy, LLC (USRC Rx), under temperature-controlled conditions. The central pharmacy will maintain the study level accountability and distribution records and will store the study drug under controlled temperature conditions. Investigator-Sponsor or its official designee will supply study drug from USRC Rx to the clinical sites. Please refer to the pharmacy manual for further information.

The Investigator or site designee will be responsible for maintaining accurate study drug patient level accountability, storage, destruction and/or return records for study drug that is received from the central pharmacy. All study drug that is received from the central pharmacy must be kept under controlled temperature in a secure, locked location in which access is limited until dispensed to the individual subject.

All unused and/or partially used study drug will be returned by the study subject for destruction at the investigational site in accordance with its policies and procedures. Records of disposal will be documented and maintained. No unused study drug may be disposed of until fully accounted for by the Investigator-Sponsor or designee. Empty containers may be disposed of in accordance with local procedures after fully accounted for by Investigator-Sponsor or designee.

The use of study drug for any reason other than as directed by the protocol is not permitted.

Refer to Section 7.4 for additional details on assessment of treatment compliance.

### **7.2.2 Formulation, Appearance, Packaging and Labeling**

Blinded study drug, (ferric citrate 1g tablets or matching placebo) will be supplied to USRC Rx in high-density polyethylene bottles. Each bottle will contain 200 tablets.

The unassigned study drug supply will be stored at the USRC Rx in its original packaging. Upon subject randomization and notification to USRC Rx, study drug may be dispensed to meet a 3-9 month supply need (per site discretion) and re-supplied as required in advance of in-person or telephone study visits.

Labeling from the manufacturer will be in accordance with current GMP requirements. The USRC Rx will generate an additional label specific to this research protocol which will not obscure the manufacturers label.

### **7.2.3 Product Storage and Stability**

Please consult the Pharmacy Manual for details on storage and temperature monitoring procedures and managing temperature excursions.

## **7.3 Measures to Minimize Bias: Randomization and Blinding**

### **7.3.1 Randomization**

Eligible subjects will be stratified by site and by eGFR (above or equal to/below 15 ml/min/1.73m^2) randomized in a 1:1 ratio to receive either ferric citrate or matching placebo. eGFR can be calculated using any commonly used method or equation for estimating eGFR.

### **7.3.2 Blinding**

This is a randomized, double-blind, placebo-controlled study. Treatment assignment will be done through a validated electronic system. The Investigator-Sponsor, Investigator, and study teams will not be aware of which treatment will be assigned next.

In case of an emergency, the Investigator has responsibility for determining if unblinding of a subject's treatment assignment is warranted. The Investigator must consult with the Medical Monitor prior to unblinding of a subject's treatment assignment. Subject safety must always be the first consideration in making such a determination. All unblinding requests should be generated within the EDC system. If it is not possible to access the EDC system, the study-specific unblinding request form can be used. If a subject's treatment assignment is unblinded, the Investigator-Sponsor must be notified within 24 hours after breaking the blind. Emergency unblinding procedure details will be provided in the Pharmacy manual. The date and reason that the blind was broken must be recorded in the source documentation and eCRF, as applicable. Unblinding a subject's treatment assignment by the Investigator or study site personnel under any other circumstances (except as noted above) will be considered a protocol deviation.

If a subject's treatment assignment is unblinded, they will be considered an early termination. The subject will permanently discontinue study drug. The subject will be followed as per instructions in Section 8.1.2.

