### **8.1.2 Permanent Discontinuation of Study Drug**

Subjects are free to withdraw from taking study drug at any time upon request. Subjects who permanently discontinue study drug will be asked to continue study participation (either by in person visits or by allowing access to medical records) in accordance with the SoA, through completion of the study. The endpoint assessment will be considered the End of Study date.

If a subject declines to continue study visits and withdraws consent to be followed, the subject is an early termination, and NO endpoint assessment will be performed. The subject's early termination date will be considered the End of Study date.

An Investigator **may** discontinue study drug or withdraw a subject from the study for the following reasons:

- Pregnancy
- Significant study intervention non-compliance
- If any clinically significant AE, laboratory abnormality, or other medical condition or situation occurs such that continued participation in the study would not be in the best interest of the subject
- Iron overload supported by liver biopsy, magnetic resonance imaging and persistent elevations in TSAT or ferritin
- If the TSAT remains >50%; Refer to Section 7.1.2.1
- If the ferritin remains >500 ng/mL; Refer to Section 7.1.2.1
- If the serum phosphorus remains <3.0 mg/dL; Refer to Section 7.1.2.1
- Investigator-Sponsor decision
- Lost to follow-up

The reason for study drug discontinuation will be recorded in source documentation and in the eCRF.

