### 3.3. Missing or Incorrect Data

Discontinuation from study intervention is different from discontinuation from the study, and remaining study procedures will be completed as indicated by the study protocol unless the subject withdraws consent for participation in the study. The date of vital status for all patients who early term will be capped at 37 days post the early termination date. For all patients who complete the study through 9 months, the 10-month follow-up safety visit date will be capped at 307 days post study drug Day 1.

All data pertaining to the primary and secondary endpoints collected at any point during the study, both during study drug treatment and post-study drug treatment discontinuation, will be used for the primary analysis of the endpoints and its individual components.

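### Protocol 7.3.2 labels an unblinded subject an early termination yet also directs follow-up under 8.1.2, so later dialysis starts, and deaths beyond the SAP's 37-day cap, can be lost

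*Protocol*

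**What the plan says.** Protocol 7.3.2 (Blinding) gives three consecutive instructions for a subject whose code is broken.

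- Status: "If a subject's treatment assignment is unblinded, they will be considered an early termination".
- Drug: study drug is stopped permanently.
- Follow-up: "The subject will be followed as per instructions in Section 8.1.2".

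Protocol 8.1.2 (Permanent Discontinuation of Study Drug) has two branches.

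- Drug stopped, consent kept: "Subjects who permanently discontinue study drug will be asked to continue study participation", by visits or record access, on the Schedule of Activities to the end of the study.
- Visits declined and consent withdrawn. If a subject "withdraws consent to be followed, the subject is an early termination, and NO endpoint assessment will be performed". For that subject the "early termination date will be considered the End of Study date".

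SAP 3.3 adds: "The date of vital status for all patients who early term will be capped at 37 days post the early termination date". It makes no exception for unblinding. For subjects who complete 9 months, the corresponding cap on the follow-up visit date is 307 days from Day 1. The same section says that "All data pertaining to the primary and secondary endpoints collected at any point during the study", on or off drug, enters the primary analysis. SAP 3.4.4 states no censoring rule, and the disposition reasons in SAP 3.5 do not include unblinding.

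**The concern.** Section 7.3.2 gives one subject the label of the second branch of 8.1.2 and the drug status of the first. A site that codes early termination in the eCRF may take participation to be over and stop recording dialysis starts, which are half of the only confirmatory endpoint. If the site does continue, the SAP cap still attaches to the label, so a death more than 37 days after unblinding can drop out of the analysis although the subject never withdrew consent.

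The code may be broken only in an emergency, so any events lost this way could come from subjects at raised risk. The loss is also avoidable. Other off-drug situations expressly keep follow-up on the Schedule of Activities (7.1.2.1 for high TSAT or ferritin, 7.5.3 for repeated transfusion, 7.5.4 for commercial Auryxia). Section 8.3 seeks dialysis, transplant and vital status even for subjects lost to follow-up. On the unfavourable reading, a consenting unblinded subject would be followed less completely than a lost one.

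**Working it through.** **The texts side by side**

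| Situation | Label | Endpoint follow-up |
|---|---|---|
| Drug stopped, consent kept (8.1.2) | permanent discontinuation | continues per schedule |
| Consent withdrawn (8.1.2, 8.2) | early termination | none (8.1.2) |
| Randomised, never dosed (6.3, SAP 3.2) | early termination | not stated |
| Code broken (7.3.2) | early termination | per 8.1.2, branch not named |

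The label has no single definition. The no-assessment rule is conditional on withdrawn consent, so 8.1.2 on its own terms keeps an unblinded subject in follow-up. The cap in SAP 3.3 is conditional only on the label. A subject unblinded on Day 60, for example, would have vital status capped at Day 60 + 37 = 97, against 307 for a completer. The cap concerns vital status only; no rule covers a dialysis start after unblinding.

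**Reproducing the plan's sample size** (Protocol 10.1: control rate 0.94 per person-year, hazard ratio 0.60, 0.75 years each, 200 per arm, two-sided 5%)

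- Placebo event probability: 1 − exp(−0.94 × 0.75) = 0.506, or 101.2 events.
- Ferric citrate: 1 − exp(−0.94 × 0.60 × 0.75) = 0.345, or 69.0 events.
- Total: 170.2 events.
- Freedman's formula needs 169 events, and 169 / 0.4254 gives N = 398, which matches the stated 400.
- Schoenfeld power with 170.2 events: Φ(√170.2 × |ln 0.60| / 2 − 1.96) = 91.5%.

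The 0.94 rate comes from a pilot composite that included transplant, so 170 may be somewhat high for this trial's endpoint.

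**Effect on power.** The documents give no number of unblindings, so the number of lost events k is an assumption. If k events are lost without changing the hazard ratio, replace 170.2 by 170.2 − k:

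| k | 0 | 4 | 8 | 12 | 20 |
|---|---|---|---|---|---|
| Power | 91.5% | 90.9% | 90.2% | 89.5% | 87.9% |

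**Effect on bias, worst case.** All k losses fall in one arm and person-time is unchanged. Under a true hazard ratio of 1 each arm has d = 101.2 events. With losses only on ferric citrate, the apparent ratio is (d − k)/d, its log has standard error √(1/(d − k) + 1/d), and the benefit-side error (nominal 2.5%) is Φ(−1.96 − ln[(d − k)/d]/SE). With losses only on placebo at a true ratio of 0.60, the apparent ratio is 0.60 × d/(d − k).

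| k | Apparent HR, true 1, lost on ferric citrate | Benefit-side error | Apparent HR, true 0.60, lost on placebo |
|---|---|---|---|
| 2 | 0.980 | 3.45% | 0.612 |
| 4 | 0.960 | 4.69% | 0.625 |
| 8 | 0.921 | 8.28% | 0.652 |

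**What the cap still catches.** At the planning rates, 1 − exp(−0.94 × 37/365.25) = 9.1% of placebo subjects and 5.6% of ferric citrate subjects (rate 0.564) would have a composite event in any 37-day window. The risk just after an emergency would be higher, and deaths in that window stay inside the cap.

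**The case against.** The case for leaving the text alone is substantial. The clause "the subject is an early termination, and NO endpoint assessment will be performed" is written for a subject who has withdrawn consent, not for everyone who carries the label. The label is used more widely: the disposition list in SAP section 5 counts endpoints among the reasons for early termination, so the label cannot by itself mean that endpoints go unassessed. Section 7.3.2 sends the reader to a section about stopping drug, whose first paragraph asks for continued participation. The 37-day cap presupposes that vital status is obtained after early termination. All of this stands, and it is why continued follow-up is the better reading.

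It does not settle the matter. The favourable branch has to be inferred, because 7.3.2 does not name it. The rule that all collected data are used governs use, not collection. The cap follows the label whichever branch the site chooses.

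A reader might go further and infer that sick subjects are censored just before death or dialysis. The documents do not support that. A death within 37 days falls inside the cap, and because the SAP states no censoring rule, censoring at unblinding is itself an inference. A reader might also infer that the loss favours the drug, because suspected drug toxicity would prompt unblinding more often on ferric citrate. The pooled NDD-CKD safety data do show more adverse events on the drug (75.3% against 61.7%, Protocol 3.3.1), but high iron indices, low phosphorus and drug-related events are handled by dose reductions or holds that do not require unblinding (7.1.2.1, 8.1.1). Unblinding needs an emergency and prior consultation with the Medical Monitor. Nothing in the documents establishes unequal unblinding.

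**Conclusion.** The contradiction in 7.3.2 is real, and SAP 3.3 gives it a consequence: dialysis starts can go unrecorded if a site acts on the label, and deaths more than 37 days after unblinding can be lost even if it does not. The likely size is small. Losing 8 of about 170 expected events costs just over one percentage point of power. The one-arm figures are worst cases that show how the direction would depend on the arm; they are not a forecast. The number of unblindings, the share of those subjects who go on to an event, and the split between arms are all assumptions. Minor severity, moderate confidence: a wording defect worth correcting, not evidence that the primary result will be biased.

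**What to change.** - **Protocol 7.3.2:** replace the early-termination statement. Say that an unblinded subject is coded as permanently discontinued from study drug, stays in the study, and has every endpoint assessment on the Schedule of Activities through Month 10 unless consent is withdrawn. The existing rule on study drug after unblinding is unchanged.
- **SAP 3.3:** state that the 37-day cap does not apply to unblinded subjects who have not withdrawn consent, and that they are analysed as randomised.
- **SAP 3.5:** list unblinded subjects by arm as a separate item.

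The cost is one sentence in a protocol amendment, short additions to the SAP and one eCRF disposition code. No visits are added beyond those already scheduled.

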## **7.4 Study Intervention Compliance**

Study personnel will instruct the subjects and caregivers on the correct number of tablets to take each day with their meals or snacks. Subjects will be instructed to return with their bottle(s) of study drug at each in-person visit so that compliance may be assessed. Unused study drug will be re-dispensed to the subject at the end of each in-person visit.

Throughout the study, subjects will be questioned regarding dosing compliance and whether they have questions or have experienced any problems related to the dosing of study drug. The Investigator or designee will also maintain study drug accountability itemizing all study drug dispensed to and returned from each subject during the study. Treatment compliance will be determined from these logs and subject questioning.

Subjects who miss doses will be counseled on the importance of compliance. Subjects will not be withdrawn from the study for reasons related to study drug compliance.

